## 5.3. Treatment and Study Procedures

### 5.3.1. Treatment

The following pacing configurations will be evaluated at the EP visit (pacing protocol):

#### **Biventricular pacing**

Pacing will be performed on one LV electrode pair (at 3 different longitudinal locations), and on the tip of the RV-lead. In total, three different pacing locations will be evaluated:

Configuration 1: RV + LV lateral Apex

Configuration 2: RV + LV lateral Mid

Configuration 3: RV+ LV lateral Base (**Reference: Standard CRT**)

Version 1.0

30/MAY/2016

Confidential

**MultiSpot simultaneous LV-ventricular pacing (MultiSpot-SYN)**

Pacing will be performed on 3 electrodes on the LV wall, placed at different longitudinal locations, and on the tip of the RV-lead simultaneously.

Configuration 4: RV + LV lateral Apex + LV lateral Mid + LV lateral Base

**MultiSpot sequential LV-ventricular pacing (MultiSpot-SEQ)**

Three electrodes on the LV wall will be paced sequentially. The RV electrode will be paced simultaneously with the last paced LV electrode. The timing-sequence and the amount of spots will depend on the electrical delays measured during the experiments.

Configuration 5: LV lateral Apex → LV lateral Mid → LV lateral Base + RV

For each pacing configuration, the evaluation of the effect of CRT will be performed approximately 4 times (repetition) in order to increase signal to noise ratio. Each setting lasts about 20 beats (10-15 sec) interspersed with baseline (AAI; also 20 beats, 10-15 sec) pacing.

Optimal AV-delay will be calculated using CardioSync™ formulas ( $PAV_{ECG} = \min(Ap-Pend + 30 \text{ ms}, Ap-RVs - 50 \text{ ms})$ ) derived from a correlation study between electrocardiographic measures such as the intrinsic AV interval and P-wave duration. PAV denotes here the optimal paced AV delay. Ap-Pend indicates the time between atrial pacing (Ap) and end of the P-wave. Ap-RVs denotes the time interval between atrial pacing (Ap) and right ventricular sensing (RVs). Up to five different AV-delays will be evaluated in this study (i.e. the optimal AV-delay and optimal AV-delay  $\pm 30$  and  $\pm 60$  ms).

Each of the five pacing configuration will be combined with each of the five AV delays. Each combination of configuration and AV delay will be repeated four times interspersed with baseline pacing.

**5.3.2. Visits and Data Collection**

CRF data will be entered and collected in Oracle Clinical. The SYNSEQ study consists of the following study visits: baseline and EP study procedure. The baseline visit can be a standalone visit or occur on the same day as the EP study. At baseline a magnetic resonance image (MRI) will be collected.

Electrophysiological data from the EP study (e.g., surface ECGs, (non-)invasive blood pressure, LV pressure, electrograms) will be collected by the scientists using a data acquisition system. The raw data will be processed by the scientists/engineers after the EP procedure, e.g., calculations of first time derivative of the LV pressure, and timing differences between electrodes on the heart or on the chest. The processed data will be provided by the scientists/engineers to the statistician(s) in Excel sheets.

**6. Determination of Sample Size****6.1. Primary Objective #1**

The sample size calculation is based on the primary objective 1 and the primary endpoint, i.e., % change LV dP/dt max from baseline (AAI setting). This study is powered to show superiority of MultiSpot SYN pacing to BiV pacing (standard CRT) for the primary endpoint % change + LV dP/dt max from baseline (AAI pacing). Assuming an expected difference in % change between MultiSpot and BiV pacing of 3.5% and standard deviation of 7%, 34 patients would have 80% power to demonstrate superiority. The total sample size is increased to 40 patients to accommodate for data collection problems during the EP

procedure. The following null-hypothesis  $H_0$  and alternative hypothesis  $H_1$  will be evaluated at a significance level of 0.05:

$$H_0: \Delta_{\text{MultiSpot SYN}} - \Delta_{\text{BiV}} = 0\%$$

$$H_1: \Delta_{\text{MultiSpot SYN}} - \Delta_{\text{BiV}} \neq 0\%,$$

where  $\Delta$  indicates percentage change from baseline for the corresponding configuration. Previous literature and results from the iSPOT study suggests that the average difference in percentage change between MultiSpot SYN and BiV pacing is 2.5% in a normal HF population (iSPOT study, Sohal, et al., 2015; Thibault, et al., 2013). For the standard deviation of the difference in % change between MultiSpot and BiV pacing we assume 7% based on previous literature and the iSPOT study.

Not much literature is available for the difference in % change between MultiSpot and BiV pacing for the study population targeted in this study. This study selects "difficult" CRT patients in order to adequately address the potential benefit of MultiSpot Pacing in this patient population. The term "difficult" represent those patients with an increased likelihood of non-response to conventional cardiac resynchronization therapy (e.g. ischemic patients or non-LBBB left ventricular dyssynchrony patients). Based on few small subgroup analyses (iSPOT study, Sohal, et al., 2015), we expect that the difference in % change between MultiSpot SYN and BiV pacing will be slightly higher in the targeted study population, namely 3.5%. The sample size calculation is based on this difference of 3.5% and a standard deviation of 7%.

## 6.2. Primary Objective #2

For the primary objective 2, previous literature suggests that the average difference in % change LV dP/dt max between MultiSpot SEQ and BiV pacing is 3% (Pappone, et al., 2014; Shetty, et al., 2014) in a normal HF population. Assuming an increased difference between MultiSpot SEQ pacing and BiV pacing within the targeted study population similar to the increase for the difference between MultiSpot SYN pacing, i.e., 1 %, the expected difference between MultiSpot SEQ pacing and BiV pacing is 4%. Assuming this difference and a standard deviation of 7%, a sample size of 34 patients has 90 % power to demonstrate superiority.

### 6.3. Secondary Objective #1

[figure not shown]
For the secondary objective 1, a power of 80% is achieved with 34 patients. Based on previous research (iSPOT study, Sohal, et al., 2015), we assume that the lower border of the 95 % confidence interval for % change MultiSpot SYN to baseline (AAI mode) in the targeted patient population is 12.6. In this study we consider MultiSpot SEQ non-inferior to MultiSpot SYN if the difference in their means is less than a quarter of the difference between MultiSpot SYN pacing and baseline. The non-inferiority margin is thus chosen to be – 3%. Assuming the expected difference in percentage change dP/dt max between MultiSpot SEQ and MultiSpot SYN pacing is 0.5% and a standard deviation in differences of 7%, 34 patients would have 80% power to demonstrate non-inferiority of MultiSpot SEQ to MultiSpot SYN.

## 7. Statistical Methods

### 7.1. Study Subjects

#### 7.1.1. Disposition of Subjects

A subject is enrolled in the study when he/she signs and dates the Patient Informed Consent. The study will enroll up to 40 subjects who fulfill the eligibility criteria and who have completed the EP study procedure. It is anticipated that this study will require approximately 12 to 18 months for subject enrollment. Patients' participation in this study is expected to last approximately between 1 day and 3 months, depending on the time between enrollment and the EP study and the duration of hospital stay after the research study, or EP related procedure, or the CRT-implant. Subjects will be exited from the study just before the moment of hospital discharge. There will be no further follow-up required for subjects that are exited from the study. A flow chart similar to Figure 1 will be created to describe patient disposition.

**Figure 1: Patient Disposition Flow Chart**

Study exits will be summarized according to exit reason. Violation of inclusion and exclusion criteria at baseline will be summarized for all enrolled patients.

The following tables will be considered to summarize patient disposition:

1. Number (%) of patients per center
2. Number (%) of patients by visit/procedure
3. Follow-up time

Follow-up time will be determined as the time between date of enrollment and date of study exit or date of last contact with subject if the subject was lost to follow-up.

### 7.1.2. Clinical Investigation Plan (CIP) Deviations

Deviations from the clinical investigation plan will be collected as deviations on the Study Deviation eCRF. Deviations will be summarized in the final report in a table by coded category. Deviation coding will be performed by Medtronic, and the coding will be collected on the MDT Deviation eCRF. The number of deviations per category, the number and percentage of subjects with a deviation in this category will be reported.

### 7.1.3. Analysis Sets

This statistical analysis plan is created to support the final analysis of the SYNSEQ study. Study manager, scientists/engineers, data manager and statistician will determine the visit cut-off date and received data cut-off date for the final data base lock as suitable.

All patients who signed the informed consent document will be defined as the enrolled population. The Analysis Population is defined as patients who are enrolled, have no inclusion or exclusion criteria violation regarding the most important criteria, i.e., inclusion criteria 1 and 2 and exclusion criterion 3, and have less than 3 months between MRI and EP visit.

The EP study visit should take place within 3 months (less than or equal to 92 days) after the MRI has been obtained. Subjects should be exited if the EP visit cannot be done within 3 months after the MRI. In the case that the subject has not been exited and EP visit data has been obtained, this data cannot be included in the analysis since it might influence the validity of results.

Patients, who are not part of the Analysis Population, will not be included in the primary analysis of the primary objectives, but will be reported in the patient disposition table (number of patients per center). A secondary analysis might be performed including patients who were excluded of the analysis cohort. Safety will be reported on the All Enrolled Population and the primary objectives will be reported on the Analysis Population.

**Table 1: Definition of Analysis Sets**

Cohort	Definition
All Enrolled	All patients that signed informed consent (i.e. informed consent date not blank)
Analysis	Enrolled Patients who have no inclusion or exclusion criteria violation regarding the most important criteria (i.e., inclusion criteria 1 and 2 and exclusion criterion 3) and who have less than three months between MRI and EP visit
Safety	All patients that signed informed consent

**Table 2: Use of Analysis Sets**

Analysis Item	Analysis set
Baseline summary	Analysis
Attrition and follow up summary	Analysis
Primary Objective #1	Analysis
Primary Objective #2	Analysis
Secondary Objective #1	Analysis
Secondary Objective #2	Analysis
Secondary Objective #3	Analysis
Adverse Event summary	Safety
Device Deficiency summary	Safety
Deviation summary	All Enrolled

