- Multi-lead ECG (within last 3 months, otherwise a new ECG should be performed)
- Echocardiographic evaluation (if available within last 3 months, otherwise not collected)
- NYHA classification
- Medical history (cardiovascular or related)
- Cardiovascular medications

- Pregnancy test for women with child-bearing potential
- MRI as explained in paragraph below

F.2.1.1 Magnetic Resonance Imaging (MRI)

Patients will undergo a baseline MRI before scheduled CRT-related surgery (i.e. dedicated research study or EP procedure or actual CRT implant) to identify the location and transmural of any myocardial scar using late gadolinium enhancement-magnetic resonance imaging according to standard hospital practice. During the MRI a thorax scan is required to be able to reconstruct the thorax and lungs, i.e. a transverse scan with neck and liver visible. An appropriate marker should be placed on the xyphoid and 10 cm above the xyphoid during this scan. In addition, left ventricular end systolic volume (LVESV), left ventricular end diastolic volume (LVEDV) and left ventricular ejection fraction (LVEF) will be determined. MRI can be performed as standard of care or solely for the study. If the patient has a LBBB conduction pattern and QRS-width above 150ms, the MRI images should be analyzed before the EP study to detect the presence of scar. If no scar is present on late gadolinium enhancement MRI, the LBBB patient with QRS > 150ms should not be included in the study (if MRI done as standard of care) or should be exited from the study (if MRI done solely for the study).

F.2.2 Electrophysiological (EP) study visit

The EP study visit can be a standalone visit or can occur on the same day as the baseline visit. The EP study visit should take place within 3 months after the MRI has been obtained. Patients will undergo standard implant of a biventricular pacing system (CRT-P or CRT-D) or will undergo the EP study (data for this research study will be collected) before possible CRT-implant or will participate in this dedicated research study as a standalone visit (without any concomitant procedure).

If available in the center, a finger volume clamp system (e.g. model Nexfin, BMEYE B.V.) will be connected to one of the subject's fingers to measure the blood pressure non-invasively. In addition, a multi-lead surface ECG is collected during the whole procedure.

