### 7.4. Handling of Missing Data and Dropouts

No imputation of missing data is planned. Study attrition of subjects will be summarized (see Section 7.1.1). For the EP study data, it can happen that a configuration cannot be applied for a certain subject or that the data collected cannot be used for analysis. For each configuration, the number of patients with this configuration available will be summarized in a table similar to Table 3. For each objective and comparison between configurations, the number of patients effectively contributing to the analysis will be reported.

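### SAP Table 2 puts the attrition and follow-up summary on the Analysis set, which omits patients who left before the EP visit and conflicts with SAP 7.1.1 and 7.1.3

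*SAP*

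**What the plan says.** SAP Table 2 lists "Attrition and follow up summary" against the Analysis set. SAP Table 1 defines that set as enrolled patients with no violation of inclusion criteria 1 and 2 or exclusion criterion 3, and "who have less than three months between MRI and EP visit". The All Enrolled set is "All patients that signed informed consent (i.e. informed consent date not blank").

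SAP 7.4 sends the reader elsewhere for the content: "Study attrition of subjects will be summarized (see Section 7.1.1"). Section 7.1.1 starts from enrolment at consent. It plans a disposition flow chart, exits by reason, counts per center and per visit or procedure, and follow-up time running from enrolment to exit or, for patients lost to follow-up, to last contact. It names all enrolled patients only for the eligibility-violation summary. SAP 7.1.3 adds that patients outside the Analysis Population "will be reported in the patient disposition table (number of patients per center").

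Two kinds of exit before the EP visit are built into the plan. SAP 7.1.3 states: "Subjects should be exited if the EP visit cannot be done within 3 months after the MRI". Under Protocol F.2.1.1, a patient with LBBB, QRS above 150 ms and no scar "should be exited from the study (if MRI done solely for the study").

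**The concern.** A patient is enrolled at consent but can enter the Analysis set only after an EP visit. An attrition summary run on that set therefore drops those who left in between before it starts counting. Their exit reasons and follow-up time are lost from the summary meant to show them.

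This matters because the SAP imputes nothing (7.4) and evaluates the primary objectives on a selected subset (7.1.3). The number lost, and why, help a reader judge that selection. A programmer who follows Table 2 as written would omit them and still comply with the SAP.

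**Working it through.** **1. Who can be in the Analysis set.** The definition needs an interval from MRI to EP visit. A patient with no EP visit has no such interval and cannot meet the condition. This follows from the wording but is not stated outright.

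**2. Which exits remain visible in that set.** SAP 7.1.1 says: "Subjects will be exited from the study just before the moment of hospital discharge". Since every member has had the EP visit, the only early exits left to count fall between that visit and discharge.

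**3. Whether other text overrides Table 2.**

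| Place in SAP | Content | Set named |
|---|---|---|
| Table 2 | Attrition and follow-up summary | Analysis |
| 7.4 | Attrition, by reference to 7.1.1 | None |
| 7.1.1 | Exits by reason; counts by visit; follow-up time | None |
| 7.1.1 | Eligibility violations | All enrolled |
| 7.1.3 | Patients outside the Analysis Population, in the disposition table | Those outside Analysis |

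Table 2 is the only place that assigns a set to attrition and follow-up. The conflict with 7.1.3 is direct, because that section includes patients whom Table 2 removes. The conflict with 7.1.1 is by implication: a clock that starts at consent, a rule for patients lost to follow-up and a count by visit have little use in a set whose members all reached the EP visit.

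**4. Size.** The documents state no attrition rate, so there is no figure to reproduce. Let E be the number enrolled, a the exits before the EP visit, and b the early exits between the EP visit and discharge. Assume everyone else qualifies for the Analysis set. Then:

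- attrition on All Enrolled = (a + b) / E
- attrition on the Analysis set = b / (E − a)

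E, a and b are all assumed. E = 50 is included because the ceiling of 40 in SAP 7.1.1 refers to patients who completed the EP procedure, so the number who consent can be higher.

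| E | a | All Enrolled, b = 0 | Analysis, b = 0 | All Enrolled, b = 1 | Analysis, b = 1 |
|---|---|---|---|---|---|
| 40 | 3 | 3/40 = 7.5% | 0/37 = 0% | 4/40 = 10.0% | 1/37 = 2.7% |
| 40 | 6 | 6/40 = 15.0% | 0/34 = 0% | 7/40 = 17.5% | 1/34 = 2.9% |
| 40 | 10 | 10/40 = 25.0% | 0/30 = 0% | 11/40 = 27.5% | 1/30 = 3.3% |
| 50 | 3 | 3/50 = 6.0% | 0/47 = 0% | 4/50 = 8.0% | 1/47 = 2.1% |
| 50 | 6 | 6/50 = 12.0% | 0/44 = 0% | 7/50 = 14.0% | 1/44 = 2.3% |
| 50 | 10 | 10/50 = 20.0% | 0/40 = 0% | 11/50 = 22.0% | 1/40 = 2.5% |

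**5. Effect on the primary analysis.** None. The row does not enter the sample size. The stated 80% power with 34 patients (difference 3.5%, SD 7%, two-sided 0.05) reproduces at 0.808 from the noncentral t distribution for a paired test.

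**The case against.** The best defence is that this is one mislabelled cell in a plan that otherwise looks at everyone enrolled. Section 7.1.1, where 7.4 sends attrition, reads naturally as covering all consented patients. Much of this stands, and it rules out three stronger readings.

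- **That the trial's reported attrition will be close to zero.** A reader might infer this from Table 2, but it holds only for that row. Eligibility violations and deviations are summarized for all enrolled patients, and adverse events and device deficiencies for everyone who consented. A disposition flow chart is also planned. The figure is missing from the text available for review, so its starting population cannot be checked and nothing can be concluded from it either way.
- **That the count per center is all the SAP gives for patients outside the Analysis set.** It is not. Table 4, on CRT response indicators, has one column for all subjects and one for those analysed (SAP 7.6), so some comparison of enrolled with analysed patients is already planned.
- **That the step from 34 to 40 patients sets the size at 6/40 = 15% against 0/34 = 0%.** SAP 6.1 gives the reason for that step as data collection problems during the EP procedure. Such patients reached the EP visit, and the SAP definition of the Analysis set does not require usable data, so this cause alone does not remove them. The row with E = 40 and a = 6 above is only an illustration.

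The defence does not remove the inconsistency. Exit reasons and follow-up time have no set named in 7.1.1, so Table 2 governs them, and 7.1.3 promises only a count per center for the patients it leaves out.

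**Conclusion.** The point holds as an internal inconsistency limited to one row of SAP Table 2. Run as written, the attrition and follow-up summary omits every patient who left before the EP visit, including those the plan requires to be exited.

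The understatement cannot be fixed from the documents. With 40 enrolled and 3 to 10 exits before the EP visit, it is 7.5% to 25% on All Enrolled against 0% on the Analysis set, provided nobody exits early between the EP visit and discharge. One such later exit would raise the Analysis-set figure to about 3%. These counts are assumptions, not plan figures.

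Severity is minor. The row affects how selection is reported. It does not change who is analysed for the primary objectives, any estimate or test, or power.

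**What to change.** In SAP Table 2, change the set for the attrition and follow-up row from Analysis to All Enrolled. In SAP 7.1.1, name All Enrolled as the set for the exit-reason, visit or procedure, and follow-up-time summaries.

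The cost is one table cell and one sentence. No new data are needed: Protocol Table 2 already schedules exit data at baseline as well as at the EP visit, and Protocol F.7 requires the withdrawal reason in the eCRF. No efficacy analysis changes.

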## 7.2. General Methodology

Data summaries for categorical data will be summarized as count, e.g., number of patients, and/or number of events, and a percentage relative to the total number of patients/events. The denominator will be explicitly identified when not clear from the context. Continuous variables will be represented by mean and standard deviation, except when the distribution of the variable is highly skewed in which case median and quartiles will be reported.

P-values for hypothesis testing will be evaluated based on two-sided testing using significance level of 0.05 except for the non-inferiority testing (secondary objective 1) which is evaluated using one sided testing and a significance level of 0.025. Confidence intervals will be reported as two-sided 95% confidence intervals.

### 7.3. Center Pooling

The study is expected to be conducted in approximately 10 centers in Europe. The data from all centers will be pooled. There will be no minimum limit that each investigator must enroll. The maximum number of enrolled subjects per center is 15 subjects.

### 7.4. Handling of Missing Data and Dropouts

No imputation of missing data is planned. Study attrition of subjects will be summarized (see Section 7.1.1). For the EP study data, it can happen that a configuration cannot be applied for a certain subject or that the data collected cannot be used for analysis. For each configuration, the number of patients with this configuration available will be summarized in a table similar to Table 3. For each objective and comparison between configurations, the number of patients effectively contributing to the analysis will be reported.

**Table 3: Number of Patients per Pacing Configuration**

Configuration	Available Patients
BiV distal	N
BiV mid	N
BiV apical	N
MultiSpot SYN	N
Multispot SEQ	N

### 7.5. Adjustments for Multiple Comparisons

Besides the comparisons between MultiSpot SEQ/SYN pacing and BiV pacing (primary objectives), there is also interest in comparing the BiV pacing configuration directly to each other. In total, ten comparison are being planned (3 for primary objective #1, 3 for primary objective #2, 1 for secondary objective #1, and three comparisons directly between the BiV pacing configurations).

No adjustment for multiple comparisons is planned due to the exploratory nature of the study.

